#### **12.1.1. Definitions**

##### **12.1.1.1. Adverse Event**

An AE is any untoward medical occurrence in a clinical study subject. No causal relationship with the study drug/ IMP or with the clinical study itself is implied. An AE may be an unfavorable and unintended sign, symptom, syndrome, or illness that develops or worsens during the clinical study. Clinically relevant abnormal results of diagnostic procedures including abnormal laboratory findings (e.g., requiring unscheduled diagnostic procedures or treatment measures, or resulting in withdrawal from the study) are considered to be AEs.

This includes the following:

- AEs not previously observed in the subject that emerge during the protocol-specified AE reporting period (see Section [12.1](#)), including medical triggers resulting in an HAE attack. Emotional stress will not be considered an AE unless it results in a medical diagnosis or requires medical treatment.
- Findings from protocol-mandated interventions. This can include laboratory assessments performed in the course of the clinical trial. AEs should only be reported if the abnormalities are changes from baseline and are clinically significant as described above.
- Pre-existing medical conditions (other than the condition being studied) judged by the investigator to have worsened in severity or frequency or changed in character during the protocol-specified AE reporting period

An adverse reaction is defined in Article 2(n) of Directive 2001/20/EC as follows: all untoward and unintended responses to a study drug/IMP related to any dose administered. The definition covers also medication errors and uses outside what is foreseen in the protocol, including misuse and abuse of the product. The definition implies a reasonable possibility of a causal relationship between the event and the study drug/IMP. This means that there are facts (evidence) or arguments to suggest a causal relationship.

For the purposes of this protocol, HAE attacks and their associated symptoms will not be defined as AEs, unless they meet the criteria for a SAE. HAE attacks and associated symptoms will be recorded in the subject's diary. The events that may trigger a HAE attack such as an infection or trauma are considered AEs and should be reported as such.

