#### **12.1.2. Method, Frequency, and Time Period for Detecting Adverse Events and Reporting Serious Adverse Events**

Reports of all AEs and SAEs, regardless of Investigator attribution, are to be collected from the time of signing of the informed consent. All AEs and SAEs are to be reported on the AE eCRF.

AEs should be documented on eCRFs as Investigators become aware of them. AEs are to be followed until the event resolves. If an event is ongoing at the last follow-up visit, Grade 1 and 2 events do not need to be followed if the event is deemed unlikely to be related or not related to study drug/IMP (see Section 12.1.3 for AE grading). For all Grade 3 and 4 events or events deemed possibly, probably or definitely related to use of study drug/IMP, the event should be followed until the AE is resolved or the subject is in a clinically stable condition with regards to the AE.

The Investigator shall report all SAEs immediately to the Sponsor by communicating with the Medical Monitor (phone or email) and by submission of an SAE report form via fax or email, and entering the event onto the AE eCRF within 24 hours of their knowledge of the event (see Section 12.1.5). The SAE report form is a detailed, written report on the SAE provided by the Sponsor or designee. The Investigator should follow all unresolved SAEs observed during the study until they are resolved, or are judged medically stable, or are otherwise medically explained.

The Investigator should attempt, if possible, to establish a diagnosis based on the presenting signs and symptoms. In such cases, the diagnosis should be documented as the AE and not the individual sign/symptom. If a clear diagnosis cannot be established, each sign and symptom must be recorded individually. Once a diagnosis is made during evaluation or treatment, the Investigator will update the AE record with this diagnosis. The immediate and follow-up reports shall be sent to the Sponsor within 24 hours to ensure that the Sponsor shall have the necessary information to continuously assess the benefit-risk profile of the study drug/IMP in clinical trial.

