### **13.2.5. Analysis of Safety Variables**

Adverse events will be mapped to a Medical Dictionary for Regulatory Activities (MedDRA) preferred term and system organ classification. Any event reported on the subject's study record that occurs on or after the initiation of study drug within a given treatment period is defined as treatment emergent. Additionally, it is assumed that an AE that is reported to have started on Day 1 without an associated onset time may have occurred after the initiation of study drug. Hence, AEs occurring on Day 1 with no associated onset time will be assumed to be treatment emergent. The occurrence of treatment-emergent AEs will be summarized by treatment group using MedDRA preferred terms, system organ classifications, and severity. Separate summaries of treatment-emergent SAEs and AEs considered to be related to study drug will be generated. All AEs will be listed for individual subjects showing both verbatim and preferred terms.

Descriptive summaries of vital signs, weight, ECG parameters, and clinical laboratory results will be presented separately for each study visit and treatment group. Laboratory abnormalities will be graded according to the DMID Adult Toxicity Table (Publish Date: Draft, November 2007, see Appendix 16.1).

Any graded abnormality that occurs following the initiation of study drug and represents at least 1-grade increase from the baseline assessment is defined as treatment emergent. The number and percentage of subjects experiencing treatment-emergent graded toxicities will be summarized by treatment group. Laboratory toxicity shifts from baseline to post baseline assessments will be summarized by study visit and treatment group. DLCO results will be presented as change from baseline in mL/min.

Clinically significant abnormal morphological ECG findings will be summarized by study visit.

Physical examination results will be presented in listings.

Concomitant medications will be coded using the World Health Organization (WHO) dictionary. These data will be summarized by treatment group.

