## **12.4. Adverse Events**

All AEs will be coded using the Medical Dictionary for Regulatory Activities (MedDRA 18.1). System organ class (SOC), high level group term, high level term, preferred term, and lower level term will be attached to the clinical database. A table showing the mappings of AE verbatim text to the coded terms will be provided.

Adverse events with an onset date and time prior to the first dose of study drug for the study will be assigned as a pre-dose AE for the listing and will not be included in the summaries.

Treatment-emergent AEs are defined as AEs that occurred on or after date of first dose of study drug and up to +30 days after the last dose. Investigators are not required to contact subjects after the last follow-up if it occurs prior to 30 days from last dose.

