### **12.4.2. Summaries of Adverse Events**

Summaries of treatment emergent AEs will be provided for the Safety Population. No inferential statistics will be provided. A brief summary of AEs will show, by treatment group, the number and percentage of subjects who 1) had any AE, 2) had any drug-related event, 3) permanently discontinued from study drug due to an AE, 4) had any serious adverse event (SAE), 5) had any Grade 3 or higher AE, 6) had any Grade 3 or higher drug-related AE, 7) had any AE leading to interruption of study drug, 8), drug related SAE, or 9) died. Drug-related events are defined as those AEs in which the Investigator believes were possibly, probably, or definitely related to the study drug.

AEs will be summarized by treatment group. For each SOC and preferred term, the number and percentage of subjects reporting an event will be calculated. In summary tables, SOCs and events within a SOC will be presented by decreasing frequency count based on the total number

of events. Multiple events (by subject or SOC as appropriate) will be counted only once per subject per dose in each summary. For summaries that use severity grade, the most severe event will be selected.

The following summary tables (number and percentage of subjects) of treatment-emergent AEs (by SOC and preferred term) will be provided by treatment group:

- Overall summary of Treatment-Emergent adverse events
- Summary of treatment-emergent adverse events
- Summary of drug-related, treatment-emergent adverse events
- Summary of treatment-emergent adverse events by severity
- Summary of treatment-emergent Grade 3 or Grade 4 adverse events
- Summary of drug-related, treatment-emergent Grade 3 or Grade 4 adverse events
- Summary of serious treatment-emergent adverse events
- Summary of treatment-emergent adverse events leading to permanent discontinuation of study drug
- Summary of treatment-emergent adverse events leading to interruption of study drug
- Summary of drug-related, treatment-emergent serious adverse events
- Summary of Treatment-Emergent Rashes Considered Related to Study Drug

Data listings will be provided for all AE data. In addition to listing all AEs, distinct data listings will also be provided for 1) Grade 3 or Grade 4 AEs, 2) AEs leading to permanent study discontinuation, 3) SAEs and deaths, 4) Rashes.

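### An AE that starts in screening and worsens on drug is left out of the treatment-emergent AE tables unless the site happens to open a new record

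*Protocol*

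**What the plan says.** **Collection.** Under Protocol 12.1.2, reports of AEs and SAEs "are to be collected from the time of signing of the informed consent". Screening lasts up to 21 days (Protocol 10.1), so AEs that are already open at first dose can be expected.

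**What an AE is.** Protocol 12.1.1.1 describes an AE as a sign, symptom, syndrome or illness "that develops or worsens during the clinical study". It also counts a pre-existing condition, other than HAE, that the investigator judges to have worsened during the reporting period.

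**What a treatment-emergent AE is.** In Protocol 13.2.5 it is a reported event "that occurs on or after the initiation of study drug within a given treatment period is defined as treatment emergent". In SAP 12.4: "Treatment-emergent AEs are defined as AEs that occurred on or after date of first dose of study drug", with a window that closes 30 days after the last dose.

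**What happens to earlier AEs.** SAP 12.4 is explicit: "Adverse events with an onset date and time prior to the first dose of study drug" "will be assigned as a pre-dose AE for the listing and will not be included in the summaries".

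**What is tabulated.** SAP 12.4.2: "Summaries of treatment emergent AEs will be provided for the Safety Population". The tables it names (all TEAEs, drug-related, by severity, Grade 3 or 4, serious, leading to discontinuation or interruption) are all of treatment-emergent AEs.

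**The concern.** The classification turns on when the event began. What happens to its severity after dosing plays no part. The AE definition in the same protocol does recognise worsening, and the laboratory rule in the same section is built on it.

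Three of the four safety endpoints in Protocol 7.2.3 are AE counts that use the treatment-emergent label: discontinuation due to a TEAE, treatment-emergent SAEs, and Grade 3 or 4 TEAEs. A symptom that was Grade 1 in screening and Grade 3 on drug is the sort of event these endpoints exist to count. Symptoms such as nausea or headache have no laboratory measure that would show the change by another route. If such an event stays on its screening record, the endpoint counts miss it.

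**Working it through.** No arithmetic decides this point, and the plan has no figure to reproduce. The check is to take six kinds of event through the written rules.

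| Case | Rule that applies | Result |
|---|---|---|
| A. AE starts after first dose | Protocol 13.2.5; SAP 12.4 | TEAE |
| B. AE starts in screening with a full start date; grade rises on drug; one record kept | SAP 12.4, onset before first dose | Listing only |
| C. As B, but the site opens a new record dated at the worsening | SAP 12.4, onset after first dose | TEAE |
| D. AE starts in screening; start day missing; start month is the month of dosing | SAP 10.1 sets the start to the day of first dose | TEAE, even with no change in grade |
| E. Laboratory abnormality present at baseline rises by at least one grade after dosing | Protocol 13.2.5; SAP 12.5.2 | Treatment emergent |
| F. AE on Day 1, timed before the first dose | SAP 12.4 defines TEAEs by date, and pre-dose AEs by date and time | Fits both categories |

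**B against C.** The clinical course is the same and the result is opposite. It depends only on how the site completes the form. I looked for a rule that settles this:

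- The worsening bullet in Protocol 12.1.1.1 concerns pre-existing medical conditions. An AE that arose after consent is already a recorded AE, so the bullet does not clearly apply, and it says nothing about a new onset date.
- Protocol 12.1.2 says how long an AE is followed, and that the record is updated once a diagnosis is made. It does not say whether a rise in grade updates the old record or opens a new one.
- SAP 12.4.2 selects the most severe event for severity tables, but only among events already classed as treatment emergent.

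**B against E.** Protocol 13.2.5 and SAP 12.5.2 call a one-grade laboratory increase from baseline treatment emergent. A one-grade symptom increase on a screening record is not.

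**B against D.** A screening AE with an incomplete date enters the tables whether or not it worsened. One with a complete date that worsened to Grade 3 does not.

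**What one subject is worth.** This shows how coarse the tables are; it does not estimate the effect. Protocol 5.3.3.1 reports three subjects with Grade 3 TEAEs, all at 350 mg, where n = 18: 3/18 = 16.7%. One more such subject gives 4/18 = 22.2%, a step of 1/18 = 5.6 percentage points. For the planned 125 mg and 250 mg groups, 14 × 3/7 = 6 in Part 2 plus 20 × 3/10 = 6 in Part 3 gives 12 each, so one subject is 1/12 = 8.3 points. The documents give neither the number of AEs open at first dose nor the number that worsened, so the number of missed events cannot be calculated.

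**The case against.** The case on the other side is substantial, and most of it stands.

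- **Other outputs catch some cases.** A reader might infer that these events vanish from every safety summary. They do not. Laboratory data have the one-grade rule and shift tables, and liver tests have fold-ULN and fold-from-baseline tables. Vital signs, ECG and pulmonary diffusion are summarised against baseline (SAP 12.6 to 12.8). SAP 11.1 tabulates reasons for stopping study drug with no treatment-emergent filter. The AE listings, including those for Grade 3-4 events and SAEs, have no such filter either, and in groups this small they can be read in full.
- **Worsening may be recorded as its own AE.** The AE definition covers worsening, and Protocol 13.2.5 speaks of an event that occurs after dosing begins. A site could properly open a new record (case C). The documents do not say that each AE must stay on one record. This limits the point to case B but does not remove it, because nothing tells sites which to do.
- **The obvious examples are largely covered.** A reader might think first of raised transaminases or abdominal HAE symptoms. Under Protocol 12.1.1.1 a laboratory finding is an AE only if it is a clinically significant change from baseline, so an on-drug rise would generally be a new event. AST or ALT at or above twice ULN at screening is an exclusion. HAE attacks and their symptoms go to the diary and are not AEs unless serious.
- **Some rules lean towards inclusion.** Day 1 AEs with no onset time count as treatment emergent, and partial dates can move to first dose. Neither helps a fully dated screening AE.
- **The tables are descriptive.** No test is run on AEs. That lowers the stakes, but the counts are still named safety endpoints.

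**Conclusion.** The point holds for non-laboratory AEs that start between consent and first dose, increase in grade or become serious on drug, and are kept on their original record. Under SAP 12.4 these are absent from the AE summary tables, and so from the three AE-based endpoints in Protocol 7.2.3. They remain in the listings, and a resulting discontinuation may show in the disposition table. SAP 12.4 is the operative text, since it states the exclusion outright; Protocol 13.2.5 contributes by having no worsening clause.

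The size is unknown and may be nil. A reader might also infer a downward bias in the Grade 3-4 and discontinuation counts that grows with dose. The direction is plausible if the drug causes the worsening, but the documents give no count from which to show that any event was missed, let alone a difference between arms.

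The conclusion assumes that no instruction outside these two documents, such as an eCRF completion guide, already requires a new record on worsening. If one does, the gap is only in the wording. The change is still worth making, because the rule as written conflicts with the plan's own AE definition and laboratory rule, and correcting it costs very little.

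**What to change.** 1. In SAP 12.4 and Protocol 13.2.5, define a TEAE as either (a) an AE with onset on or after the first dose and up to 30 days after the last dose, or (b) an AE with onset before the first dose that increases in severity grade or becomes serious within that window. This also gives both documents the same window.
2. In SAP 12.4, limit the pre-dose, listing-only category to AEs that do not meet (b). Use first-dose date and time, where known, in both definitions, so that a timed Day 1 pre-dose AE falls in one category only. Keep the existing rule for Day 1 AEs with no time.
3. In the AE recording rules (Protocol 12.1.2), state that such worsening is entered either as a new AE record dated at the worsening or as a dated grade change on the existing record. Choose one, so that sites do the same thing and the programming can follow it.

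**Cost.** A sentence or two in each document and a short eCRF completion note. TEAE counts may rise slightly in any arm, placebo included. For subjects already treated, dates of worsening may need a query to the site if only the highest grade was captured.

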### **13.2.6. Pharmacokinetic Analysis**

Concentrations of BCX7353 will be determined by validated plasma assays and will be summarized by treatment and displayed in figures. Plasma PK parameters for each subject will be estimated over the sampling interval using non-compartmental analysis (WinNonlin v 6.3 or higher, Pharsight Corp) and summarized by treatment and dose using descriptive statistics.

The PK parameters that may be estimated are listed in [Table 7](#). Additional analyses may be conducted as appropriate.

**Table 7: Pharmacokinetic Parameters**

Pharmacokinetic Parameter	Definition
$AUC_{\tau}$	Area under the plasma concentration versus time curve over the dosing interval ( $\tau$ ) (i.e., 24 hours for once daily dosing)
$C_0$	Observed concentration predose
$C_{av,ss}$	Average steady-state plasma drug concentration during multiple-dose administration
$C_{max}$	Maximum observed concentration of drug
$C_{\tau}$ (steady state only)	Observed drug concentration at the end of the dosing interval ( $\tau$ )
CL/F	Apparent oral clearance after administration of the drug calculated as $Dose/AUC_{\tau}$
$\lambda_z$	Terminal elimination rate constant, estimate by log linear regression of the terminal elimination phase of the concentration of drug versus time curve
$V_z/F$	Apparent volume of distribution of the drug
$t_{1/2}$	Estimate of the terminal elimination half-life of the drug
$T_{max}$	Time of $C_{max}$

In all derivations of PK parameters, zero will be substituted for concentrations below the quantification limit (BQL) of the assay. Samples which are BQL, but are between 2 samples with detectable concentrations will be excluded from PK analysis.

Dose proportionality will be analyzed using a power model and an ANOVA model based on dose normalized PK parameters. Additional analyses may be conducted as appropriate.

### 13.2.7. Pharmacodynamic Analysis

On-treatment plasma kallikrein inhibition data will be expressed as percent inhibition compared to subject baseline activity. Ex vivo plasma kallikrein activity will be listed by subject, treatment, day, and time and summarized separately by treatment, day, and time. Descriptive statistics will be reported. Mean and individual plasma kallikrein inhibition versus time profiles will be plotted by treatment group.

C1 INH functional levels and absolute change from baseline will be summarized.

### 13.2.8. Pharmacokinetic/Pharmacodynamic Analyses

Exposure-response analyses of the relationships between plasma kallikrein inhibition, efficacy endpoints and BCX7353 plasma concentrations may be explored using model-based techniques as applicable.

### **13.2.9. Quality of Life Analyses**

The change from baseline in the domain scores of the AE-QoL (function, fatigue, nutrition & fear/shame) and the DASS (depression, anxiety, stress) as well as the composite score of each instrument will be compared between the treatment and placebo groups. Individual items will be plotted to understand their contribution to the domain sub-scores.

## **14. STUDY ADMINISTRATION**

### **14.1. Regulatory and Ethical Considerations**

#### **14.1.1. Regulatory Authority Approvals**

This study will be conducted in compliance with the protocol; Good Clinical Practices (GCPs), including International Conference on Harmonization (ICH) of Technical Requirements for Registration of Pharmaceuticals for Human Use Guidelines (ICH E6); EMA regulatory requirements; and in accordance with the ethical principles of the Declaration of Helsinki. In addition, the study will be conducted in compliance with all applicable local laws and regulatory requirements relevant to the use of new therapeutic agents.

#### **14.1.2. Institutional Review Board and Ethics Committee Approvals**

Before initiation of the study at an investigational site, the protocol, the ICF, the subject information sheet (if applicable), and any other relevant study documentation will be submitted to the appropriate IRB/IEC. Written approval of the study must be obtained before the study center can be initiated or the study drug can be released to the Investigator. Any necessary extensions or renewals of IRB/IEC approval must be obtained, in particular, for changes to the study such as modification of the protocol, the ICF, the written information provided to subjects, and/or other procedures. After the protocol has been submitted, any amendment must be agreed by the Investigator after discussion with the Sponsor and will be formally documented. All substantial amendments will be submitted for an opinion as required by current regulations.

The IRB/IEC will be promptly provided any new information that may adversely affect the safety of the subjects or the conduct of the study. On completion of the study, the IRB/IEC will be provided with a report of the outcome of the study.

Written reports of clinical study status will be submitted to the IRB/IEC annually or more frequently if requested by the IRB/IEC. A final study notification will also be forwarded to the IRB/IEC after the study is completed or in the event of premature termination of the study in accordance with the applicable regulations. The study will be considered to be completed once the last subject completes their last study visit. Copies of all contact with the IRB/IEC should be maintained in the study file. Copies of clinical study status reports (including termination) should be provided to BioCryst.

